Appendix

6-minute walking test Detailed instruction for challenge:

I. GENERAL INSTRUCTIONS

The Six Minute Walk Test Form is filled out by the study clinician conducting the test. Using a paper copy of the form to record the data while the test is in progress is recommended.

The Six Minute Walk, an assessment of lung function is the Flexible Block A procedure. Usually the walk should follow shortly after spirometry since it is performed after bronchodilation (for participants with COPD and/or asthma).

The testing area must be a 30m (100 ft.) segment of straight, unimpeded hallway.

Prepare the area by applying markers for the endpoints and 3m intervals to the baseboard on one side of the hall, with special attention to avoid doorways, etc.

Use the provided 30m metric tape measure. If a pre-existing 100 ft. (30.48m) course with 10ft. markers has been previously laid out, it may be used.

If available, place the traffic cones at the center of the proximal and distal turn points. Place the turn signs at the proximal and distal turn points of the course.

Have ready the following materials: stopwatch/timer, worksheet for counting laps, oximeter, Borg breathlessness and exertion scales, a chair that can be easily moved along the walking course, emergency equipment (according to local policy): telephone, sphygmomanometer, oxygen source.

A “warm-up” period before the test should not be performed.

Participants should use their usual walking aids during the test (cane, walker, etc.) and be dressed in comfortable clothing and walking shoes.

II. DETAILED INSTRUCTIONS FOR CHALLENGE

Read the following instructions to the participant:

“The object of this test is to walk as far as possible for 6 minutes. You will walk back and forth in this hallway. Six minutes is a long time to walk, so you will be exerting yourself. You will probably get out of breath or become exhausted. You are permitted to slow down, to stop, and to rest as necessary. You may lean against the wall while resting, but resume walking as soon as you are able. You will be walking back and forth around the cones. You should pivot briskly around the cones and continue back the other way without hesitation. Now I’m going to show you. Please watch the way I turn without hesitation.”

Demonstrate by walking one lap yourself. Walk and pivot around a cone briskly.

Record completed and partial laps on the lap count worksheet.

Say to the participant:

“Are you ready to do that? I am going to use this counter to keep track of the number of laps you complete. I will click it each time you turn around at this starting line. Remember that the object is to walk AS FAR AS POSSIBLE for 6 minutes, but don’t run or jog. Start now, or whenever you are ready.”

Standardized Encouragement read in a steady voice:

- After the 1st minute: “You are doing well. You have 5 minutes to go.”
- When the timer shows 4 minutes remaining: “Keep up the good work. You have 4 minutes to go.”
- When the timer shows 3 minutes remaining: “You are doing well. You are halfway done.
- When the timer shows 2 minutes remaining: “Keep up the good work. You have only 2 minutes left.
- When the timer shows 1 minute remaining: “You are doing well. You only have 1 minute to go.

- With 15 seconds to go: “In a moment I’m going to tell you to stop. When I do, just stop right where you are and I will come to you.”
- At 6 minutes: “Stop”

If the participant stops at any time prior, you can say: “You can lean against the wall if you would like; then continue walking whenever you feel able.”

Do not use other words of encouragement (or body language) to influence the patient’s walking speed. Accompany the participant along the walking course, but keep just behind them. Do not lead them.

III. DETAILED INSTRUCTIONS FOR EACH ITEM

Before starting:

Item 1. Pulse: Record beats per minute.

Starting test:

Item 2. Start of 6-minute walk: Record time in hours and minutes. Choose AM or PM.

Immediately following 6MW: Record the following:

Item 3. Pulse: Record beats per minute.

Item 4. Breathlessness: Record participant’s response from 0-10 on the Modified Borg Scale (0=no breathlessness, nothing at all, 0.5=very, very slight, 1=very slight, 2=slight breathlessness, 3=moderate, 4=somewhat severe, 5=severe breathlessness, 6=is between severe breathlessness and very severe breathlessness, 7=very severe breathlessness, 8=between very severe breathlessness and very,very severe breathlessness, 9=very, very severe breathlessness, 10=maximum breathlessness.)

Item 5. Exertion: Record participant’s response from Scale of Perceived Exertion (0=none, 2=very,very light, 3=very light, 4=fairly light, 5=somewhat hard, 6=hard, 7=very hard, 8=very,very hard.

Item 6. Type of course used: Select the type of course used. Record 1 for 30 meters x 2 lengths, 2 for 100 feet x 2 lengths, or 3 for other. If Other, specify in the space provided.

Item 7. Record the number of completed laps

Item 8. Record the distance walked the final partial lap in meters.

Item 9. Stopped before 6 minutes: Record Y for Yes or N for No. If No skip out of form. If Yes answer Item 10 and 11.

Item 10. Duration: Record in minutes and seconds.

Item 11. Reason for stopping: Record one response 1-5. (1=desaturation <80%, 2=foot, knee, hip or other orthopaedic pain, 3=muscle fatigue or pain, 4=breathlessness, 5=adverse event)

Item 12. If response to Item 11=5, select all that apply. (a=angina, b=lightheadedness, c=intolerable dyspnea, d=leg cramps, e=staggering, f=diaphoresis, g=pale or ashen appearance, h=mental confusion or headache, i=other). If other is selected, please explain.

Appendix

Name:
Date:

Overall Neuropathy Limitations Scale (ONLS)

Instructions: The examiner should question and observe the patient in order to determine the answers to the following questions. Note should be made of any other disorder other than peripheral neuropathy which limits function at the foot of the page.

ARM SCALE

Does the patient have any symptoms in their hands or arms, eg tingling, numbness or weakness? Yes No
(if "no", please go to "legs" section)

Is the patient affected in their ability to:	Not affected	Affected but not prevented	Prevented
Wash and brush their hair			
Turn a key in a lock			
Use a knife and fork together (or spoon, if knife and fork not used)			
Do or undo buttons or zips			
Dress the upper part of their body excluding buttons or zips			
If all these functions are prevented can the patient make purposeful movements with their hands or arms?	Yes 	No 	Not applicable 

Arm Grade

- 0= Normal
- 1= Minor symptoms in one or both arms but not affecting any of the functions listed
- 2= Disability in one or both arms affecting but not preventing any of the functions listed
- 3= Disability in one or both arms preventing at least one but not all functions listed
- 4= Disability in both arms preventing all functions listed but purposeful movement still possible
- 5= Disability in both arms preventing all purposeful movements

SCORE= _____

LEG SCALE

	Yes	No	Not applicable
Does the patient have difficulty running or climbing stairs?			
Does the patient have difficulty with walking?			
Does their gait look abnormal?			
How do they mobilise for about 10 metres (ie 33 feet)?			
Without aid			
With one stick or crutch or holding to someone's arm			
With two sticks or crutches or one stick or crutch holding onto someone's arm or frame			
With a wheelchair			
If they use a wheelchair, can they stand and walk 1 metre with the help of one person?			
If they cannot walk as above are they able to make some purposeful movements of their legs, eg reposition legs in bed?			
Does the patient use ankle foot orthoses/braces? (please circle)			 If yes: (please circle) right/left

Leg grade

- 0= Walking/climbing stairs/running not affected
- 1= Walking/climbing stairs/running is affected, but gait does not look abnormal
- 2= Walks independently but gait looks abnormal
- 3= Requires unilateral support to walk 10 metres (stick, single crutch, one arm)
- 4= Requires bilateral support to walk 10 metres (sticks, crutches, crutch and arm, frame)
- 5= Requires wheelchair to travel 10 metres but able to stand and walk 1 metre with the help of one person
- 6= Restricted to wheelchair, unable to stand and walk 1 metre with the help of one person, but able to make some purposeful leg movements
- 7= Restricted to wheelchair or bed most of the day, unable to make any purposeful movements of the legs

SCORE= _____

Overall Neuropathy Limitation Scale= arm scale (range 0 to 5)+leg scale (range 0 to 7);
(range: 0 (no disability) to 12 (maximum disability))

TOTAL SCORE= _____

Is there any disorder, other than peripheral neuropathy, which affects the above functions Yes No
If yes please describe

1 INTRODUCTION

The objective of this Statistical Analysis Plan (SAP) is to ensure the maximum credibility of all study findings. This plan will not repeat all the definitions given in the protocol, but will provide further details of the analyses planned therein.

This Statistical Analysis Plan was prepared and signed prior to the database lock after all patients had completed the study.

This SAP has been written in agreement with:

- The Study Protocol version 4.0 dated 10FEB2017
- The Case Report Form (CRF) version 1.0 dated 16MAY2019.

1.1 Study objective

The primary objective of the study is to assess the effect of MD1003 on motor and sensory conduction, in patients suffering from demyelinating polyneuropathies.

The secondary objective is to evaluate safety of MD1003 in this patient population.

This pilot study is not controlled by a placebo. It is aiming to evaluate the acceptability of the treatment in this population, to assess the intra and inter-individual variability of the neurophysiological procedures proposed in this study protocol, and to assess the robustness of the evaluation criteria. The results will serve as hypothesis for the sample size calculation of a larger placebo controlled trial.

1.2 Study design

This is a pilot, open label, uncontrolled monocentric study in 3 distinct groups of patients suffering from a specific aetiology pattern of peripheral neuropathy:

- Chronic inflammatory demyelinating polyradiculoneuropathy (CIDP)
- Demyelinating neuropathy associated with immunoglobulin M (IgM) monoclonal gammopathy and antibodies against myelin-associated glycoprotein (anti-MAG)
- Charcot-Marie-Tooth 1a and 1b (CMT1a and CMT1b) neuropathy

The total study duration is expected to be 52 weeks: 4 weeks for baseline period and 48 weeks for treatment period. The study flow-chart is presented below:

	Week -4	Week 0	Week 12	Week 24	Week 36	Week 48
	Selection	Inclusion	Follow-up			End
STUDY WINDOWS		+/-5 days	+/-10 days			+/- 15 days
Informed consent	X					
Inclusion criteria	X	X				
Non-inclusion criteria	X	X				
Medical history	X					
Clinical examination	X	X	X	X	X	X
Neurophysiological examination		X		X		X
MRC sum score		X	X	X	X	X
INCAT sensory Score		X	X	X	X	X
Posturography score		X		X		X
ONLS score		X	X	X	X	X
Timed 10-meter walk test		X	X	X	X	X
6-min walk test		X	X	X	X	X
Excitability testing		X		X		X
AEs reporting		X	X	X	X	X
Concomitant therapies	X	X	X	X	X	X
Biological test ¹	X ²					X
Serum sample	X			X		X
Study drug dispensation		X	X	X	X	
Compliance check			X	X	X	X

¹ Biological safety panel includes: RBC, hemoglobin, mean corpuscular volume, WBC, platelets, electrolytes (Na, K, HCO₃, Ca), protein, creatinine, glomerular filtration rate, fasting blood glucose, AST, ALT, total and free bilirubin, gamma glutamyl transferase, alkaline phosphatase, triglyceride, cholesterol, PT, aPTT, INR

² Biological aetiology additional panel: Serum protein electrophoresis, IgA measurement, HbA1c, HBsAg, HIV, HCV tests, fibrinogen

Six visits were planned:

- Visit 1: Selection visit at W-4
- Visit 2: Inclusion visit at W0
- Visit 3 at W12 ± 10 days
- Visit 4 at W24 ± 10 days
- Visit 5 at W36 ± 10 days
- Visit 6: last visit at W48 ± 15 days

Actually, a unique visit was performed for visit 1 and visit 2 (see section 2.1).

1.3 Sample size

This pilot study is exploratory. The various clinical and electrophysiological endpoints allowed to define which of them would be the most relevant in a larger randomized controlled trial.

It was assumed that 15 patients was a sufficient sample size to 1) detect a signal of clinical efficacy of MD1003 in demyelinating peripheral neuropathies, and 2) rank clinically the best

endpoints for confirmatory studies in the three most common demyelinating peripheral neuropathies.

The study included 15 patients in total divided into 3 subgroups of 5 patients suffering from either CIDP, anti-MAG or CMT1a/CMT1b.

2 SUMMARY OF CHANGES TO THE PROTOCOL

2.1 Changes to the conduct of the study

Classical MRC sum score with 6 muscles was planned in the protocol for the assessment of muscle strength. In the context of peripheral neuropathies an extended version of this MRC involving 19 muscles was used.

Safety data were to be reviewed on a regular basis by the Data Safety Monitoring Boards (DSMB) (see protocol section 11.8.2). It was the Sponsor decision not to implement a DSMB in this open labelled non-controlled study based on FDA's guidance for clinical Sponsor "Establishment and Operation of Clinical Trial Data Monitoring Committees".

Weight measurement is not in the investigator day to day practice and was omitted.

Posturography was not performed in the same conditions as described in the protocol as the equipment available on site (dynamometric platforms Bertec 400*600mm (Bertec Corporation, Columbus, OH, USA) with a recording frequency of 1000 Hz) is different.

Data related to the center of pressure of the Posturography parameters were collected instead of data related to center of gravity.

Additionally, in agreement with the sponsor, the trial site has merged the selection visit with the inclusion visit for all the patients, leading to a single one-day visit.

2.2 Changes to the conduct of the analysis

The name of "ITT population" has been replaced by "FAS population" to be compliant with the ICH guidelines.

As sensitivity analysis of the efficacy endpoints, a Wilcoxon signed rank test will be performed to assess if the changes from baseline at week 48 in the efficacy criteria are statistically significant considering an alpha level of 5%.

Regarding secondary efficacy criteria, missing data at week 48 will be imputed considering LOCF approach.

3 GENERAL STATISTICAL CONSIDERATIONS

3.1 Hypothesis and significance level

Statistical tests will be conducted two-sided with a significance level of 5%. A resultant probability value of $p < 0.05$ will be judged as being of statistical significance.

3.2 Handling of missing data

To calculate age of the patients, if the month and year of the birth are available, the day of birth will be imputed to the 15th of the month of the birth.

The last observation carried forward (LOCF) approach will be used to handle missingness on the primary evaluation criteria at week 48 (Motor nerve conduction velocity, Distal latency, F wave latency and Length of motor nerve potential). Missing data at week 48 will be replaced by the last available post-baseline value.

Other missing or inconsistency data, especially for the secondary criteria, could be reviewed before the database lock, during the data review meeting, and the management of their imputation will be discussed. Following data review meeting, an imputation considering LOCF approach will be performed regarding missing data of secondary criteria at week 48.

Missing or incomplete dates will be managed as below:

To define Treatment Emergent Adverse Events, missing dates of study drug intake or adverse events will be replaced.

- Missing dates of the first study drug intake

In case of completely missing dates of the first study drug intake, it will be considered equal to the day of the inclusion visit + 1 day at the morning.

If the day and the month are missing:

- If the year is the same as the year of the first study drug intake, it will be estimated by the day of the inclusion visit + 1 day at the morning
- If the year is after the year of the inclusion visit, it will be estimated by the 1st January at the morning

If only the day is missing:

- If the month/year are the same as the month/year of the inclusion visit, it will be estimated by the day of the inclusion visit + 1 day at the morning.
- If the month/year are after to the month/year of the inclusion visit, it will be estimated by the first day of the month at the morning.

If only the time of first study drug intake is missing, it will be considered at the morning.

- Missing dates of the last study drug intake

In case of completely missing dates of the last study drug intake, it will be considered as the date of study completion/discontinuation – 1 day at the evening.

If the day and the month are missing:

- If the year is the same as the year of date of study completion/discontinuation, it will be estimated by the study completion/discontinuation date – 1 day at the evening

- If the year is before the year of the study completion/discontinuation date, it will be estimated by the 31 December at the evening.

If only the day is missing:

- If the month/year are the same as the month/year of the study completion/discontinuation, it will be estimated by the date of study completion/discontinuation – 1 day at the evening.
- If the month/year are prior to the month/year of the study completion/discontinuation, it will be estimated by the last day of the month at the evening.

If only the time of the last study drug intake is missing, it will be considered at the evening.

▪ Missing start dates of adverse events

In case of completely missing date, it will be estimated by the date of the first study drug intake.

If the day and the month are missing:

- If the year is the same as the year of the first study drug intake, it will be estimated by the date of the first study drug intake
- If the year is prior to the year of the first study drug intake, it will be estimated by the 31 December
- If the year is after the year of the first study drug intake, it will be estimated by the 1st January

If only the day is missing:

- If the month/year are the same as the month/year of the first study drug intake, it will be estimated by the date of the first study drug intake
- If the month/year are prior to the month/year of the first study drug intake, it will be estimated by the last day of the month
- If the month/year are after the month/year of the first study drug intake, it will be estimated by the first day of the month

If after imputation, the estimated start date is after the end date of the adverse event, it will be replaced by the end date of the adverse event.

▪ Missing end dates of adverse events

In case of adverse event not “ongoing” (i.e. ‘Recovered/Resolved’, ‘Recovered/Resolved with sequelae’ or ‘Fatal’ in the CRF) at the end of the study and end date completely missing, it will be estimated by the last available date (last visit, last examination, date of completion/discontinuation or last study drug intake).

If the day and the month are missing:

- If the year is the same as the year of last available date, it will be estimated by the last available date
- If the year is not the same as the year of last available date, it will be estimated by the 31 December

If only the day is missing:

- If the month/year are the same as the month/year of last available date, it will be estimated by the last available date
- If the month/year are not the same as the month/year of last available date, it will be estimated by the last day of the month

If after imputation, the estimated end date is before the start date of the adverse event, it will be replaced by the start date of the adverse event.

▪ Missing start/end dates of concomitant treatments

When the start or end date is partially or completely missing, the same rules as for start and end date of adverse events will be applied.

To calculate the time since the first appearance of symptoms and the time since the progression, if the date of the first appearance of symptoms or date of the progression is incomplete, it will be replaced as below:

If the day and the month are missing, it will be estimated by the 15th June

If only the day is missing, the day will be estimated by the 15th of the corresponding month.

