The allocation of patient's number will be done at the first visit (V1/selection) in chronological order of signature of the informed consent form. Once patient numbers are assigned, they cannot be reassigned. Information on the randomization number and treatment number for the whole study will be given by the investigator. The patient's initials (the first letters of the patient's name and first name) may be collected in the CRF.

5.3.4 *Screen failures*

Patients who sign an informed consent form but fail to meet the eligibility criteria are defined as screen failures. For all screen failures, the investigator is asked to maintain a screening log that documents the screening number (patient's number), patient's initials and reason(s) for screen failure. A copy of this log should be retained in the investigator's study file. The demography, the eligibility and end of trial forms will be completed and returned to the sponsor for screen failures.

5.3.5 *Withdrawal of participation or arrest of treatment of an included patient*

5.3.5.1 *Withdrawal by the patients*

Participation in the study is voluntary. The patients have the right to withdraw from the study at any time for any reason. If a patient chooses to withdraw, he must inform the Investigator immediately.

5.3.5.2 *Reasons for treatment arrest*

The Investigator has the right to terminate the treatment of any patient at any time if it is deemed to be in the patient's best interest.

Main reason for premature treatment discontinuation is the occurrence of a Serious Adverse Event (SAE) attributed to the treatment; the investigator must inform the sponsor of these SAE and follow them until resolution.

The reasons and circumstances for premature treatment discontinuation will be documented in the patient's CRF at time of withdrawal.

It is important to distinguish the following situations:

- Temporary cessation of treatment, the investigator must document the reason(s), the stop date and the restart date
- Early termination of treatment. In this case, the investigator must:
 - Document the reason(s) of early termination (effectiveness or failure of treatment), SAE (s), non-compliance of the patient to visits, other medical problems, patient personal reasons)
 - Make every effort to convince the patient to have a last visit to evaluate at least safety data and if possible efficacy data.
 - Make every effort to convince the patient to have a safety follow-up in the case of AE.

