5 PROTOCOL DEVIATIONS

A protocol deviation is defined as any changes in the study design, study conduct and/or procedures that are not in accordance with the protocol and any study materials originally approved by the Independent Ethics Committee (IEC)/Institutional Review Board (IRB).

A major protocol deviation is defined as a deviation which may affect the subject's rights, safety or well-being or the completeness, accuracy and reliability of the study data and so likely to bias significantly the interpretation of the primary efficacy criterion results.

All protocol deviations will be reviewed, in particular but not limited to:

- Deviations in inclusion and exclusion criteria
- Study treatment duration different from 48 weeks (336 days) \pm 15 days (considering interruption periods if applicable)
- Study treatment interruption > 10 consecutive days
- Deviations in study drug intake/compliance (see section 10, compliance < 80% and > 120% on 48 weeks period)
- Non respect of visit schedule (see section 1.2)
- Intake of concomitant prohibited treatments (See protocol section 5.5),
- Missing or incomplete evaluation of the primary efficacy criterion.

All protocol deviations will be reviewed before study database lock and their grade (minor / major) will be classified before the statistical analysis, during the data review meeting.

The number and percentage of patients having at least one protocol deviation (minor and/or major) and at least one major protocol deviation will be described on the Included Set by disease group and overall.

All deviations will be also listed.

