12.1 Extent of exposure

The extent of exposure (weeks) will be calculated as (date of last study drug intake – date of first study drug intake + 1) / 7

The cumulative dose per patient (g) will be calculated as (actual number of capsules taken x 100mg) / 1000, with actual number of capsules taken calculated as defined in section 11.

Descriptive statistics will be tabulated by disease group and overall on Safety Set population and a listing will be given.

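### SAP 3.2's rule for a missing last-dose date suits adverse events but, if it also feeds exposure, overstates it for early stoppers who stay in the study; two neighbouring date rules need repair (minor)

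*SAP*

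**What the plan says.** **Purpose.** SAP 3.2 opens the dose-date rules with: "To define Treatment Emergent Adverse Events, missing dates of study drug intake or adverse events will be replaced".

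**Last dose.** "In case of completely missing dates of the last study drug intake, it will be considered as the date of study completion/discontinuation", less one day, in the evening. A date known only to the year becomes that same date if the year is the completion year, and 31 December if it is an earlier year. If only the day is missing and the month precedes the completion month, "it will be estimated by the last day of the month at the evening".

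**Where a last-dose date is used.**
- SAP 12.1: "The extent of exposure (weeks) will be calculated as (date of last study drug intake" minus the first-intake date, plus 1, divided by 7.
- SAP 11: actual treatment duration is that exposure less interruption days, each interruption being counted from its restart date. The theoretical capsule count uses the first and last intake dates and their times of day.
- SAP 5 lists for deviation review "Study treatment duration different from 48 weeks (336 days", with a tolerance of 15 days either way, and separately compliance below 80% or above 120%.

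**Stop dates.** Protocol 5.3.5.2 says: "Temporary cessation of treatment, the investigator must document the reason(s), the stop date and the restart date". For early termination and loss to follow-up it asks for reasons and a last evaluation, without naming a stop date.

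**First dose, year only.** The first branch begins "If the year is the same as the year of the first study drug intake" and gives the day after the inclusion visit. The second branch, for a year later than the inclusion visit's, gives 1 January.

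**Symptom onset and progression.** "If the day and the month are missing, it will be estimated by the 15th June"; if only the day is missing, the 15th of the month is used. SAP 8 computes time since each event as selection-visit date minus event date plus 1, over 365.25.

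**The concern.** A late last-dose date is the cautious choice for classifying adverse events, because it widens the treatment-emergent window. For exposure it works the other way: a patient who stopped treatment early but stayed in the study is credited with drug that was not taken. Nothing in SAP 11 or 12.1 corrects this. A permanent stop has no restart date, so it is never subtracted as an interruption, and the date is not limited by a recorded stop or by the capsules supplied. The same date lengthens the compliance denominator, so a patient who took every capsule until stopping looks non-adherent.

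With five patients per disease group, one such patient visibly shifts a group mean. The two neighbouring rules are separate slips in the same section: one tests a date against itself, and the other can produce an impossible negative duration.

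**Working it through.** **Does the imputed date reach exposure?** SAP 3.2 imputes morning or evening as well as the day. The treatment-emergent window in SAP 12.2 is counted in whole days, so time of day has no use there; the only formulas that use it are the capsule counts in SAP 11. SAP 12.1 uses the same last-intake date and gives no other rule if it is missing. Reuse is therefore very probable, though not written.

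**The plan's own figure.** 48 × 7 = 336 days, as SAP 5 states. With 15 days' tolerance the range is 321 to 351.

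**Worst case.** Assumptions: inclusion visit day 0, first dose day 1, last dose day 30 with the date wholly missing, study completion day 336, three capsules a day, all unused capsules returned.
- Imputed last dose: 336 − 1 = day 335.
- Exposure: (335 − 1 + 1)/7 = 47.9 weeks. True: 30/7 = 4.3 weeks. Ratio 335/30 = 11.2.
- Completion on day 321 to 351, and first dose on day 0 or 1: 45.7 to 50.1 weeks.
- Duration check: 335 lies within 321 to 351 and passes; the true 30 days would be flagged.
- Compliance: 90/(335 × 3) = 90/1005 = 9.0%. True: 90/90 = 100%. If none of the first 270 capsules came back, 270/1005 = 26.9%.
- Cumulative dose, from capsule counts: 90 × 100/1000 = 9.0 g, unaffected by the date. Full treatment would be 336 × 3 × 100/1000 = 100.8 g.
- End of the treatment-emergent window: day 335 + 30 = 365 instead of 30 + 30 = 60.
- Mean exposure, other patients at 48 weeks: group of five, (4 × 48 + 47.9)/5 = 48.0 against (4 × 48 + 4.3)/5 = 39.3; all 15, (14 × 48 + 47.9)/15 = 48.0 against (14 × 48 + 4.3)/15 = 45.1.

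**Milder cases, same true stop on day 30.**

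| What is known | Imputed exposure (weeks) |
|---|---|
| Left the study on day 31 | 30/7 = 4.3 |
| Left the study on day 44 | 43/7 = 6.1 |
| Left the study on day 84 | 83/7 = 11.9 |
| Month of last dose known | at most about 60/7 = 8.6 |

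**First-dose rule.** The year being tested is the recorded year of first intake, and it is compared with the year of first intake. The condition is always true. When the recorded year is later than the inclusion visit's, both branches apply: one gives the day after inclusion, the other 1 January of the recorded year. The remaining branches compare with the inclusion visit, which shows the intent. Imputed adverse-event start dates depend on this date.

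**Progression date (visit dates are illustrative, non-leap year).**
- Year only, visit 2 January of that year: (day 2 − day 166 + 1)/365.25 = −163/365.25 = −0.45 years.
- Year only, visit 15 March: (74 − 166 + 1)/365.25 = −91/365.25 = −0.25 years.
- Month known, visit on the 2nd of that month: (2 − 15 + 1)/365.25 = −0.03 years.

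**The case against.** The strongest reply is that SAP 3.2 states its purpose as defining treatment-emergent events. Sections 8, 9, 10.1 and 12.2 refer back to 3.2 when they rely on it; sections 11 and 12.1 do not. This stands: use for exposure is an inference. But if it is not intended, exposure and compliance have no rule for a missing date, so the SAP needs a sentence either way.

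The 11-fold figure is also a constructed extreme. Protocol 5.3.6 asks for the final assessments on the last dosing day or soon after, when possible, which would usually bring completion close to the stop. Protocol 5.3.5.3 does ask withdrawn patients to return on the scheduled dates, so the long gap is possible but not typical.

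A reader might go further in three ways that the documents do not support:
- *Such patients escape detection.* They pass the duration check only. Compliance of 9% (or 27%) falls below 80% and goes to deviation review, and a 9 g cumulative dose is reported as well. What goes wrong is the reason shown: poor adherence instead of short treatment.
- *The safety rates are distorted.* SAP 12.2 reports numbers and percentages of patients and event counts. No exposure-adjusted rate is planned, so exposure is context, not a denominator. SAP 6 also reports the median, which is 48 weeks either way in the group of five.
- *Early stoppers are the ones with missing dates.* Protocol 5.3.5.2 names a stop date only for temporary cessation, but the CRF is not available here and SAP 11 presumes a last-intake date and time for every patient.

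On progression dates, SAP 3.2 allows other missing or inconsistent data to be discussed at the data review, and only a descriptive baseline variable is affected. The adverse-event rules order start against end dates; they offer no selection-visit cap to copy directly.

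**Conclusion.** The point holds as a minor correction. SAP 3.2 gives a last-dose date suited to adverse-event classification, and the SAP leaves open, while strongly implying, that the same date drives exposure, treatment duration, compliance and the duration check. If so, exposure is overstated and compliance understated for a patient who stops drug but stays in the study. The range runs from almost nothing (leaving near the stop), through at most about 30 days (month known), to 47.9 against 4.3 weeks. That extreme needs a date that is wholly missing, or known only to the year of completion, and follow-up to week 48. The number of such patients is not given and may be zero.

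The self-referring condition in the first-dose rule is an error as written, whatever the data. The mid-year rule can give a negative time since progression, and nothing in SAP 3.2 prevents it.

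**What to change.** 1. State that the present last-dose rule applies to treatment-emergent classification only.
2. For exposure, actual treatment duration, the compliance denominator and the SAP 5 duration check, impute the last intake as the earlier of (i) completion or discontinuation minus 1 day and (ii) the visit or contact at which a permanent stop was first recorded. Use the full supply dispensed only as an outer limit: a single dispensing of 270 capsules covers 270/3 = 90 days.
3. Do not subtract returned capsules in that limit, because compliance would then be computed against itself. For example, take full dosing to week 36 (252 × 3 = 756 capsules), then half doses to day 336 (84 × 1.5 = 126), 882 in all. A net-of-returns cap gives 882/3 = 294 days, compliance 882/882 = 100% instead of 882/1008 = 87.5%, and a false duration deviation, since 294 < 321.
4. Report with the exposure table (14.5.1) how many dates were imputed.
5. In the first-dose rule, compare the recorded year with the year of the inclusion visit.
6. Cap imputed symptom-onset and progression dates at the selection visit, and do not let progression precede onset.

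In the worst case above, a stop first recorded at a week-12 visit on day 84 would give 84/7 = 12.0 weeks: still above the true 4.3, but far below 47.9, and now flagged by the duration check.

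The cost is a few sentences in the SAP and a few lines of programming. SAP 11 already uses dispensed and returned capsules, and Protocol 5.3.5.2 already asks for the circumstances of early discontinuation to be documented in the CRF. Reported exposure may become slightly less favourable.
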